**If there are no personnel on your study that meet the above criteria, leave this section blank.**

Name	Institution	Telephone	E-mail	Role
------	-------------	-----------	--------	------

No External Personnel has been added to this IRB Study

Please describe the study responsibilities and qualifications of each affiliated person listed above:

## 18.0 End of Study Application

### End of Study Application Form

#### To continue working on the Study Application:

Click on the section you need to edit in the left-hand menu. Remember to save through the entire Study Application after making changes.

#### If you are done working on the Study Application:

**Important:** Before proceeding, please go back to Section 4.0 Initial Screening Questions and **Save and Continue** through the form to make sure all the relevant sections and questions have been included. If you've changed any answers since you started, the branching may have changed. Your application will be incomplete and it will have to be returned for corrections.

Once you are sure the form is complete, click **Save and Continue**. If this is a new study, you will automatically enter the **Initial Review Submission Packet Form**, where you can attach **consent forms** or other **study documents**. Review the **Initial Review Submission Checklist** for a list of required attachments.

**Answer all questions and attach all required documents to speed up your approval.**

The UCSF IRB welcomes feedback about the IRB Study Application Form. Please click the link to answer a [survey](#) about the application form.

Analysis Plan

Development and Feasibility of Mindfulness Based Pain Reduction

NCT 04980612

6/12/2019

Overall Analysis Approach: Preliminary analysis will be performed to confirm that key data variables are clean and complete. As this is not an efficacy study, we do not expect statistical significance but will estimate standardized effect sizes (Cohen's d with 95% confidence intervals). The principal analysis will use intent-to-treat methods, in which all observations will be included for individuals, regardless of adherence to the treatment protocol. As a secondary analytic method, we will also perform-as-treated analyses with those who attend at least 5 of 8 planned group sessions. We recognize the challenge of *missing data*. We will take concerted steps to limit missing data. We have extensive experience in study retention; in a current study of a mindfulness intervention by [name] (R61 AT009333), outcome assessment was completed in 97% of participants at 12 weeks. Finally, where appropriate, we will perform multiple imputation methods to address the effects of missing data if indicated.

Hypothesis Testing:

Hypothesis 1: The MBPR intervention is feasible and acceptable, and Hypothesis 2: Recruitment and randomization are feasible: We plan detailed assessments of feasibility and acceptability of the intervention, recruitment, and randomization. Domains and measures we will address are summarized in the table below.

Table : Feasibility and acceptability assessment

Feasibility Questions	Feasibility Measures
Can I recruit my target population?	Number screened per month; number enrolled per month; average time to enroll enough participants to form classes. Number of enrolled participants from each outreach method.
Can I randomize my target population?	Proportion of eligible screens who enroll during randomization phase. Acceptability from participant interviews.
Can I keep participants in the study?	Retention rates for study measures; reasons for dropouts.
Will participants do what they are asked to do?	Proportion of participants who attended at least 6 sessions. Average number of MBPR sessions attended; reasons for missed sessions. Average minutes of daily/weekly meditation practice (using data from the "Insight Timer" app)
Can the treatment be delivered per protocol?	Fidelity assessments using MBI:TAC and intervention content checklist, both using video recordings of teachers.
Are the assessments too burdensome?	Proportion of planned pre- and post-intervention assessments completed, duration of assessments, and quantitative and qualitative participant feedback.
Are the treatment conditions acceptable to participants?	Acceptability ratings; qualitative participant assessments; reasons for dropouts.
Are the treatment conditions credible?	Perceived benefit at end course and likelihood of recommending to a friend or family member (net promoter score) at the end of the course during randomized phase.
Is EMA assessment of pain intensity/interference feasible?	Proportion of EMA assessments responded to (we hypothesize that this will be > 80%). Qualitative data on acceptability.
Is assessment of meditation adherence with app feasible?	Correlation of meditation sessions measured with Insight Timer with self-report of practice during the same week; qualitative interviews.

Hypothesis 3: MBPR participants will improve in key pain outcomes. Our planned primary outcome measures in future trials will be pain interference (RTF) and pain intensity (NRS); pain acceptance and quality of life will be secondary outcomes. We will conduct exploratory hierarchical linear modeling¹⁵⁵ to examine the extent to which participants experience changes in pain interference at the end of the intervention and at 6-month follow-up (separate for EMA and questionnaires). For both pain outcome variables (pain interference, pain intensity) separate multilevel models will be estimated. The pain measure models will take into account that the present data set is organized within three different levels and that single observations (i.e., rating at a particular time during the day)(Level 1) are nested within days (i.e., rating on day 1-7 in week 1 or 8 of intervention)(Level 2), which are nested in variations of MBPR per

course (Level 3). As this is not an efficacy study, we will primarily report standardized effect sizes (Cohen-*d*) with 95% confidence intervals, based on standard deviation at baseline. Similar models for secondary outcomes will include pain acceptance, and quality of life as outcomes, each in a separate correlation.

Hypothesis 4: Assessment of pain intensity/interference with a smartphone delivered EMA is feasible and correlates with standard pain outcome measures. Feasibility/acceptability measures are noted in the table above. We will assess the correlation of our EMA measures with the Numeric Pain Rating Scale for pain intensity, and pain interference rating. We predict a correlation of >.7. We will also perform qualitative assessment to get participants assessment of where the two approaches are similar, and where they may get differing responses.

Hypothesis 5: Assessment of meditation practice adherence is feasible using a smartphone app. At the 8-week assessment period, we will include questions about meditation practice over the prior week and compare this with the results from use of the Meditation Insight Timer data. We will ask further questions about any sessions that were not recorded using the app, and reasons for not recording. This information will be analyzed after each group, and refinements made if needed in participant instructions and other steps to encourage use of the app as consistently as possible.

Hypothesis 6: We will conduct **exploratory analyses** to test for correlations between changes in pain outcomes and scores on the PCS, TSK, CPAQ, MAIA, and FFMQ using regression models.

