### 7.2 AIMS: List the specific aims:

**Specific Aim 1:** To refine and manualize an 8-week **MBPR (Mindfulness-Based Pain Reduction)** program for patients with cLBP, integrating mindfulness with (1) interoceptive awareness, i.e. cultivating a direct, non-judgmental sensory attention focus on the location of their cLBP, (2) yoga practices targeting cLBP, and (3) elements of both chronic pain education and CBT, i.e., modifying maladaptive cognition and behavior. In Phase 1 we are convening a panel of behavioral and yoga therapists with expertise in chronic pain education and management to obtain expert advice on MBSR optimization and produce a first draft of the new MBPR manual.

**Specific Aim 2:** To refine **ecological momentary assessments (EMA) measures of key pain outcomes and mobile technology measures of adherence to MBPR home practice.** EMA is emerging as a key tool for measuring pain outcomes and home practice in clinical trials, but measures are poorly standardized and validated. We will compare pain questionnaires and EMA and ensure that an EMA measure is refined and vetted before use as a clinical trial outcome. We will test a meditation timer mobile app to measure adherence.

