## **done solely for research purposes and those that are happening as part of routine care.**

Please call our office at [contact] and ask to speak to someone on the Expedited Review team if you need help differentiating between what parts are research and what parts aren't.

At UCSF:

As we described in the application for Phase 1 of this study, **MBSR** is a standardized and manualized 8-week program, delivered once a week in 2½-hour group sessions and a daylong retreat. It trains individuals in several mindfulness practices, e.g. focus on breath, varying degrees and directions of object orientation, open monitoring of awareness of intero- and exteroceptive stimuli and thoughts, de-reification (i.e. the notion that thoughts and perceptions are not always true to reality), and meta-awareness (i.e., awareness of thinking) in addition to focused attention. The program typically includes an audio-recording and a book for home practice and has shown benefits in patients with cLBP.

**MBPR** will be an optimized mindfulness program specifically designed for treating cLBP that we aim to develop and test in this project. The format is the same as MBSR: 8 weeks of weekly 2½-hour group sessions and a daylong retreat in smaller groups: 10 participants per class to allow for more individualized support. All sessions include training to enhance mindful interoceptive awareness through focused attention in the region of pain, the lower back. Key goals are to reduce avoidance, rumination, catastrophizing, and fear of movement, all key mechanisms of action in MBSR or CBT. The new elements of these classes will include more pain-specific education and key elements of CBT, enhance mindful interoceptive awareness and an expanded yoga component, for which we will provide videos for home practice.

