In addition, we will identify potentially eligible participants through review of our Medical Center's electronic medical records and send *letters inviting study participation using* the UCSF CTSI. Randomization for the final cohort will be performed using a computer-based assignment program, in which study staff must enter the participant ID number before randomization is revealed; assignment is then locked into the database. It will be stratified by sex, as responsiveness to mind-body interventions varies by sex. The UCSF study site of the ongoing NIH HEAL BACPAC initiative, for which both Drs [name] and [name] are key personnel, will create a large cohort of patients with cLBP (recruitment started June 2021), which can be approached for advertising our study.

MBPR will be delivered by an experienced mind-body practitioner with expert skills in mindfulness, MBSR and body awareness-enhancing approaches. Phase 1 includes a 2-day training retreat for the instructor led by [name] to prepare the MBSR instructor for the MBPR program. Home practice will be supported by audio recordings uploaded to the Insight Timer® smart phone platform. The Insight Timer application will also be used to track and record the frequency in which participants are doing a meditation practice in combination with a physical or electronic log. The instructor will use a workbook, audio recordings of guided meditation (these are standard recordings used e.g. in MBSR classes at the Los Angeles Insight Meditation Center), *Outsmart your Pain* by [name], PhD, a guide book for mindfulness with pain, and videos of yoga sequences (as outlined in handout, attached). Study participants will receive additional printed and audio support material.

**Schedule of Measures:** Participants will be assessed using computer-assisted questionnaires in the first and last week of the MBPR courses and will be followed up at 6 months for clinical outcomes. In addition we will use a mobile platform-based EMA, as detailed below.

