**Meditation home practice adherence measure:** *Rationale:* All participants will be instructed to do daily home practice. Benefits of any mind-body intervention may depend on applying the class teaching to practice at home. Home practice for chronic conditions may need a higher dose than e.g. for experimental pain. We will request a minimum of 30 minutes for an expected effective duration of 20 minutes (>70%) on at least 5 days per week. *Methods:* Our research team has successfully used the free downloadable mobile app InsightTimer® to monitor adherence to home practices by asking participants to use it during home practice session. It has a variety of bell sounds that can be set for desired meditation time periods. The application includes two other features we have successfully tested at UCSF: 1) It connects with the research team in our study providing data about when and for how long a participant practiced meditation. 2) The app allows guided meditation recordings that we are preparing for home practice to be uploaded and made available to participants. Participants will log in with unique pseudonyms and a participant-specific e-mail address that is created for this study only to eliminate any risk to loss of privacy, which will be discussed during the consent process. Any identification of the

participating InsightTimer user will not be possible as the app will not use the personal e-mail of the participant and only use pseudonyms.

At the VA:

This study includes a Pain Attention Task to be preformed in the fMRI that separates insula activation during experimental heat application between different pain attention conditions.

The participants will be patients with cLBP according to the definition of the NIH Task Force on Research Standards for cLBP: pain at least half the days in the past 6 months, by using 2 questions and a human figure drawing illustrating the region between the lower posterior margin of the rib cage and the horizontal gluteal fold. Participants will have an average pain intensity in the past week of at least 4 out of 10 on the numeric rating scale (NRS). They will be recruited through advertisement in newspapers, social media and fliers, and from the current UCSF Spine Center cLBP cohort (see below).

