**4.6 Fluctuations in Pain Levels:** Study physician [name] will weekly review the class reports and videos. He will be available by cell phone for more urgent problems between in-person consultations. Primary care physicians for each participant will receive information about the study before the participant begins the study. Study physician will help to make sure that primary care physicians are informed of any medical changes, and will consult with primary care physicians where indicated.

**4.7 MBPR and MBSR:** Similar interventions have been used with thousands of persons, including many with serious illness and pain conditions, and there have not been important adverse events reported to our knowledge. Participants can experience restlessness during the meditation practices or become aware of distressing emotions and traumatic memories. Our instructors are highly trained and experienced and will immediately inform the study physician, who will determine whether referral to behavioral medical care is warranted.

**4.8 Home Exercise Components:** Participants will be requested to do yoga-style exercises at home. Some people may experience initial discomfort when increasing their level of physical activity. There may also be a slight increase for physical risks when partaking in exercise activities. There are minor risks of injury during exercise, but these risks are minor and far out-weighed by the potential benefits of exercise.

**4.9 Audio/Video-Taping Instructors During Classes:** classes will be audio-videotaped to ensure intervention fidelity and provide feedback and troubleshooting for instructors. Some participants may experience a level of discomfort while being recorded during class. Although the recorders will be placed in front of the class to record the instructors' voice, there is a strong likelihood that some of the participants' movements and voices will be recorded. They may also feel that they are being monitored. Participants will be informed of the recording, and can sit farther from the microphone if they desire. Recordings will be kept on a HIPAA-compliant research network drive with password-restricted access limited to study staff. Recordings will be destroyed once the study is complete. Adverse event/unanticipated problems

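### The SAP summarises home practice only as average app-recorded meditation minutes, which does not show how many participants met the protocol's practice request, and no quantitative measure of home yoga is described

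*SAP*

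**What the plan says.** The SAP's feasibility table has a row on whether participants do as they are asked. In that row, class attendance gets two summaries: the proportion attending at least 6 sessions, and the average number of MBPR sessions attended. Home practice gets one: "Average minutes of daily/weekly meditation practice (using data from the 'Insight Timer' app").

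The request itself is in Protocol section 7.9, in the paragraph on the meditation home practice adherence measure: "We will request a minimum of 30 minutes for an expected effective duration of 20 minutes (>70%) on at least 5 days per week". The same paragraph says of the app: "It connects with the research team in our study providing data about when and for how long a participant practiced meditation". Earlier in section 7.9 the app is to be used to "track and record the frequency in which participants are doing a meditation practice in combination with a physical or electronic log".

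On yoga, the data and safety monitoring plan (DSMP), section 4.8, states: "Participants will be requested to do yoga-style exercises at home". Protocol section 7.9 lists among the new elements of the classes "an expanded yoga component, for which we will provide videos for home practice". Specific Aim 1 (section 7.2) names yoga targeting low back pain as one of three elements to be integrated with mindfulness, and Specific Aim 2 concerns "mobile technology measures of adherence to MBPR home practice".

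**The concern.** The study exists to establish feasibility; sections 9.3 and DSMP 6.2 say that it does not test efficacy. Section 7.9 itself suggests that benefit may depend on practising at home. Whether people practised as requested is therefore a main thing to learn before a trial of MBPR against MBSR.

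The request is a rule about days and duration. A mean of minutes does not show how many people satisfied such a rule, because a few heavy users can offset many light ones, and long sessions on few days can offset missed days. The SAP already handles attendance in the more informative way, with a proportion against a threshold beside the mean.

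For yoga the gap is in the data. If participants meditate at home but do not do the yoga, nothing quantitative in the plan would show it. The team would have no planned count to guide refinement between classes, or to describe how much of this component was practised outside class.

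**Working it through.** **Is there a figure to reproduce?** No. Neither document states a target proportion, pass mark or precision for home practice. The check is a search for relevant measures, followed by arithmetic on the request.

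**Step 1: where home practice is measured.**

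| Place | What is measured | Shows attainment of the 5-day request? | Covers home yoga? |
|---|---|---|---|
| SAP table, row on doing as asked | Average app meditation minutes | No | No |
| SAP table, row on the app, and Hypothesis 5 | App-recorded against self-reported meditation at 8 weeks | No; it tests the tool | No |
| Protocol 7.9, app and log | Frequency, dates and durations of meditation | Data would allow it; no summary is defined | Not described |
| Protocol 7.11, instrument list | No practice or yoga questionnaire named | No | No |
| DSMP 6.1.2 | Attendance list | No | No |

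**Step 2: the request as a weekly total.** 30 min × 5 days = 150 min/week, or 150/7 = 21.4 min/day averaged over the week. With the 20-minute effective duration it is 20 × 5 = 100 min/week.

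**Step 3: what a mean of 150 min/week can hide.** These are illustrative classes of 10; the patterns are assumptions.

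| Pattern | Mean (min/week) | Meet 30 min on ≥5 days | Meet 20 min on ≥5 days |
|---|---|---|---|
| All do 30 min on 5 days | 30 × 5 = 150 | 10/10 | 10/10 |
| All do 75 min on 2 days | 75 × 2 = 150 | 0/10 | 0/10 |
| Four do 50 min daily; six do 16.7 min once | (4 × 350 + 6 × 16.7)/10 = 150 | 4/10 | 4/10 |
| All do 25 min on 6 days | 25 × 6 = 150 | 0/10 | 10/10 |

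The same mean fits 0% to 100% attainment. The last row shows that the choice between 30 and 20 minutes can itself change the answer completely, so the SAP has to state it.

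**Step 4: would a proportion be informative at this sample size?** The planned numbers are 40 MBPR participants and 10 per class (Protocol 9.1). The Wilson 95% interval is [p + z²/2n ± z√(p(1−p)/n + z²/4n²)] / (1 + z²/n), with z = 1.96. The observed rates are assumptions.

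| Observed proportion | n = 40 | n = 10 |
|---|---|---|
| 50% | 35% to 65% | 24% to 76% |
| 70% | 55% to 82% | 40% to 89% |

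Pooled over the MBPR classes the estimate is useful for planning. By class it is only descriptive. The interval treats participants as independent, so clustering by class would widen it. Participant-weeks (up to 40 × 8 = 320) are repeated within person, so the simple formula does not apply to them.

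**The case against.** Several objections carry weight.

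- **The data exist.** A reader might infer that the study cannot show days of practice per week. The documents do not support that for meditation: section 7.9 has the app and a log tracking frequency, and the app supplying dates and durations. What is missing is a stated summary.
- **No pass mark.** A reader might infer that feasibility (Hypothesis 1) could be wrongly declared on home practice. The SAP sets no threshold for minutes, and 150 min/week is not a criterion anywhere. Home practice is also one of several measures in a ten-row table. A misleading impression is a risk only.
- **The request is loosely worded.** It gives two durations and sits beside an instruction to practise daily. Scoring from app records alone would also count unrecorded sessions as missed, although Hypothesis 5 expects such sessions and plans to ask about them. This stands and shapes the fix.
- **Yoga.** A reader might infer that yoga is what separates MBPR from MBSR, or that home yoga leaves no trace in the study. Neither follows. DSMP 4.5 treats yoga-type movement as part of both programmes, and the yoga in MBPR is expanded alongside other new elements. Exit interviews (24 of the 50 participants, section 10.14) and 6-month qualitative questions may touch on it, and the log and interview guides are not in these documents. Specific Aim 2 goes on to name a meditation timer as the adherence tool, so measuring meditation matches how that aim is carried out. No amount of home yoga is stated, so there is nothing to score it against.

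It remains that home practice is summarised only by a mean, and that no quantitative record of a requested component is described.

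**Conclusion.** The point holds in two limited parts. First, the only planned summary of home practice does not show how many participants met the request in section 7.9; a mean equal to the full request is compatible with 0% to 100% meeting it. Second, no quantitative measure of home yoga is described, although it is requested and is a named, expanded MBPR element.

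The consequence is an uninformative adherence result for planning the next trial. It biases no estimate and does not show that any conclusion on Hypothesis 1 would be false. The practice patterns and observed rates used above are assumptions. The range of 0% to 100% shows what a mean can hide, not what is likely here. The change is worth making because the meditation part needs no new data and adherence measurement is one of the study's aims.

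**What to change.** **Meditation (SAP wording only).** Keep average minutes. In the same table row:

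1. Add the proportion of participants, and of participant-weeks, meeting the section 7.9 request. Use the requested 30 minutes on at least 5 days as the main definition and the 20-minute effective duration as a sensitivity version. State over how many of the eight weeks a participant must meet it to count.
2. Compute it from app dates and durations. In a second version, add log-only or self-reported sessions, so that unrecorded practice is not scored as no practice.
3. Report it pooled over MBPR classes with a 95% interval, and descriptively by class and arm. For participant-weeks, use an interval that allows for repeated weeks within person.

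Section 7.9 should also make clear what its bracketed percentage refers to: 20/30 is 66.7%, which does not agree with >70% if that ratio is meant.

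**Home yoga (small data addition).** Add a line for days and minutes of home yoga to the existing log, and a matching item to the 8-week practice question. Report it descriptively in the same row, since the documents state no amount to judge it against.

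**Cost.** The first part costs some SAP text and a derived variable. The second costs one log line and one question, with slightly more participant burden.

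### Correlation is the only quantitative statistic the SAP names for checking Insight Timer and EMA, so a constant or proportional bias in either would not be quantified

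*SAP*

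**What the plan says.** **Purpose.** Specific Aim 2 (Protocol 7.2) sets out to compare pain questionnaires with EMA and to "ensure that an EMA measure is refined and vetted before use as a clinical trial outcome". It also says a timer app will be tested as a measure of adherence.

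**Insight Timer.** The SAP feasibility table lists "Correlation of meditation sessions measured with Insight Timer with self-report of practice during the same week", together with qualitative interviews. It sets no threshold. Under Hypothesis 5, participants report their practice over the week before the 8-week assessment, and the team will "compare this with the results from use of the Meditation Insight Timer data". The method of comparison is not stated. The SAP adds: "We will ask further questions about any sessions that were not recorded using the app, and reasons for not recording". It continues: "This information will be analyzed after each group, and refinements made if needed in participant instructions". Protocol 7.9 also provides for a paper or electronic practice log alongside the app.

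**EMA.** SAP Hypothesis 4 correlates EMA with the numeric rating scale (NRS) for intensity and with an interference rating, and states "We predict a correlation of >.7". The other EMA checks are a response rate, hypothesised to exceed 80%, and qualitative feedback on where the two methods agree or differ.

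**How app data are used.** The SAP table reports "Average minutes of daily/weekly meditation practice" from the app as a feasibility result. Protocol 7.9 asks for home practice on at least 5 days per week. Both concern absolute amounts.

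Neither document names a mean difference, limits of agreement, an absolute-agreement ICC or a concordance coefficient for either tool.

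**The concern.** Correlation describes how closely two measures follow a straight line. It does not show whether they give the same value. If EMA reads a fixed amount below the NRS, or the app captures a fixed share of practice, r is unaffected.

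That matters because both results feed the next trial. App minutes and sessions will be read as how much people practised, and EMA is a candidate outcome. A level bias would distort the practice estimates and any reading of EMA against NRS cut-offs. A scale difference would also distort change scores. Hypothesis 5 collects information that could size the app's shortfall, but the SAP does not commit to turning it into a number. For EMA there is no comparable question.

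r also depends on the spread of the sample, so comparing an estimate from about 40 people with .7 says little by itself, in either direction.

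**Working it through.** **1. The plan's own figures.** The .7 is a prediction with no derivation, so there is nothing to reproduce. The only power figure near this topic (DSMP 6.2: N = 40, r = 0.43, two-sided 0.05, 80%) does reproduce: Φ(atanh(0.43)·√37 − 1.96) = Φ(2.797 − 1.960) = 79.9%. It concerns change-score correlations tested against zero and is not an input here.

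**2. What r cannot see.** For y = a + bx with b > 0, corr(x, y) = 1 whatever a and b are. Likewise, shifting or rescaling either of two imperfectly correlated measures leaves r unchanged.

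**3. EMA with a constant offset.** Lin's concordance is CCC = 2·r·s₁·s₂ / (s₁² + s₂² + d²). The documents give no SDs, so equal SDs of 1.5 or 2 points and offsets d of 0, 1 or 2 points are assumed.

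| r (unchanged by d) | SD | d = 0 | d = 1 | d = 2 |
|---|---|---|---|---|
| 0.70 | 1.5 | 0.70 | 0.57 | 0.37 |
| 0.70 | 2 | 0.70 | 0.62 | 0.47 |
| 0.80 | 1.5 | 0.80 | 0.65 | 0.42 |
| 0.80 | 2 | 0.80 | 0.71 | 0.53 |

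Example: r = 0.80, SD 2, d = 2 gives 6.4 / (4 + 4 + 4) = 0.53.

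**4. App under-recording.** This was simulated with weekly sessions capped at 7 and mean/SD set to 5/1.5 or 4/2 (assumed).

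| App behaviour | r | CCC | Mean bias, sessions/week |
|---|---|---|---|
| Logs a fixed 50% for everyone | 1.00 | 0.23–0.42 | −2.5 to −2.0 |
| Loses 2 sessions each, floored at 0 | 0.98–1.00 | 0.50–0.62 | −2.0 to −1.9 |
| Misses 20% at random | 0.79–0.88 | 0.64–0.80 | −1.0 to −0.8 |
| Misses 50% at random | 0.54–0.68 | 0.20–0.38 | −2.5 to −2.0 |

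Random loss does lower r. Only constant or proportional loss is invisible or nearly so.

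A narrower spread makes the point about sample dependence. Assume sessions X ~ Binomial(7, 0.7), at most one a day, with 20% missed at random.
- Var X = 1.47. The recorded count is Binomial(7, 0.56), with variance 1.725.
- r = 0.8·1.47 / √(1.47·1.725) = 0.74.
- Mean difference = 3.92 − 4.90 = −0.98 sessions per week.
- The share reaching 5 per week falls from 65% to 34%.
- A person practising exactly 5 days is recorded at 5 with probability 0.8⁵ = 33%.

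**5. Precision of r.** For observed r = 0.70, tanh(atanh(0.70) ± 1.96/√(n − 3)) gives 0.50 to 0.83 at n = 40 and 0.52 to 0.82 at n = 50.

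**6. Range restriction.** Assume pain with mean 5 and SD 2 before selection, and a cut-off of 3 (Protocol 9.7). The variance ratio after truncation is u = 1 − 0.2876 − 0.2876² = 0.630. If the analysed score itself were truncated, a true r of 0.75 becomes 0.75·√u / √(1 − 0.75² + 0.75²·u) = 0.67. But 9.7 selects on a separate past-month rating. If that rating correlates ρ with both measures, r becomes (0.75 − 0.370ρ²) / (1 − 0.370ρ²). This gives 0.72, 0.71, 0.69 and 0.67 for ρ = 0.5, 0.6, 0.7 and 0.8. So 0.67 is the bottom of the range for these values. Protocol 7.9 states a different entry threshold in its VA part (at least 4, past week); the figures here use 9.7.

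**7. What the added analysis would deliver at n = 40.** With r = 0.70 and equal SDs s, the SD of differences is s·√(2·0.30): 1.16 for s = 1.5 and 1.55 for s = 2.
- 95% CI for the mean difference: ±1.96·SD/√40 = ±0.36 to ±0.48 points.
- Limits of agreement: ±1.96·SD = ±2.3 to ±3.0 points around the mean difference.
- Uncertainty of each limit: about ±1.96·SD·√(3/40) = ±0.6 to ±0.8 points.

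**The case against.** A reader might infer that both tools are validated by correlation alone and that a biased tool would pass. The documents do not support that. For the app, the same table cell adds qualitative interviews. Hypothesis 5 asks directly about unrecorded sessions and acts on the answers after each group, and a log is kept. No correlation threshold is set for the app, so there is nothing to pass. For EMA, .7 is a prediction and not an acceptance rule.

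Further points on the plan's side:
- Hypothesis 4 is a convergent-validity statement, for which correlation is a conventional statistic. Aim 2 never claims that the tools are interchangeable with self-report or the NRS.
- Levels are not hidden. Protocol 7.13 plans means and proportions, app minutes are reported, and SAP Hypothesis 3 models EMA and questionnaires separately. A large gap could be spotted, though no comparison of levels is specified.
- A constant EMA offset cancels in pre-post change and in between-arm contrasts using the same instrument. A scale difference does not.
- Bland-Altman analysis needs common units. The EMA response scale is not given, and the instrument list (Protocol 7.11) includes PEG and PROMIS-29 for interference, so the method may be undefined there.
- Self-report is an imperfect reference, so an app difference mixes missed logging with over-reporting.
- This is a feasibility study of 50 people that disclaims efficacy testing.

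All of this stands, and it limits the point. It does not supply a quantitative measure of bias for either tool.

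**Conclusion.** The point holds in a limited form. Correlation is the only quantitative statistic named for comparing each tool with its reference, and it cannot detect a constant or proportional bias. That follows from algebra and needs no assumption.

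The size does rest on assumptions. With SDs of 1.5 to 2, a 2-point EMA offset leaves r at 0.80 while concordance drops to 0.42–0.53. An app logging a fixed half of sessions gives r = 1.00 with a shortfall of 2 to 2.5 sessions per week. The fixed-half case is deterministic and chosen for illustration; random loss would show up as a lower r.

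EMA is the stronger half, because its only other checks are response rate and qualitative feedback. For the app, the planned questions, interviews and log may well reveal under-recording, and what is missing is a number for it. A reader might also infer that the pain entry criterion will push a good EMA measure below .7. The fall from 0.75 to 0.67 is a worst case under the assumed values, and interference has no entry cut-off. The change is worth making, but the study's feasibility aims do not depend on it.

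**What to change.** In the SAP feasibility table and under Hypotheses 4 and 5:

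- **Both tools:** keep r and report it with its 95% CI.
- **EMA intensity versus NRS:** for matching weeks, add the mean difference between the EMA weekly mean and the NRS, with 95% CI and Bland-Altman limits of agreement. Name the questionnaire item and its recall period.
- **EMA interference:** do the same only if both measures use the same scale and recall period. Otherwise report r with its CI and say why agreement is not assessed.
- **Insight Timer:** add the mean difference in weekly sessions versus self-report, with limits of agreement. From the Hypothesis 5 questions, add the proportion of sessions the app did not record. State that self-report is an imperfect reference, so the difference shows disagreement and not which source is wrong.

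The cost is SAP wording and a few lines of analysis on data already planned. The downside is that limits of agreement will be wide at about 40 participants. They should be reported as estimates with their uncertainty and not turned into a pass/fail rule.
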